**Inclusion Criteria**

1. 13-18 years old; males and females
2. High school soccer players from Marsh Valley High School in Idaho
  - a. In season, competition and practices at least 6-days/week

**Exclusion Criteria:**

Exclusion criteria: non-adolescents; untreated or underlying metabolic or cardiovascular diseases; allergies to dairy, or any allergies ingredients in the study provided granola bar or bagels, such as soy, wheat, tree nuts, peanuts, milk, and sesame.

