## Background and Introduction

---

Proper recovery from exercise training is necessary for training adjustments to occur and for performance to be maintained or improved. Dietary amino acid (the ‘building blocks’ of protein) intake has long been known to be important in the recovery process in order to repair damaged proteins and create new proteins that are important to athletic training and performance (Trommelen & Van Loon, 2016). Muscle recovery is regulated, in part, by nutrient availability, hormones, and inflammation, and is needed for improving a muscle’s ability to perform well. Because diet directly affects nutrient availability and sleep influences hormones and inflammation, diet and sleep are critical health behaviors involved in muscle recovery. Sleep loss can worsen inflammation (Thomas, Motivala, Olmstead, & Irwin, 2011). Protein supplementation and whey protein in particular, is a common sports nutrition strategy for making new proteins in combination with resistance exercise training (Cermak, Res, de Groot, Saris, & van Loon, 2012). During a soccer game, different efforts of exercise are important in raising sport performance. Protein supplementation has been shown to increase new proteins in cells in already trained muscles (Kritikos et al., 2021; Wilkinson et al., 2008). There is also an important link between the greatest amount of oxygen someone can use by their muscles (VO2max) and distance covered by players during a soccer match (Hoff, 2005). Evidence also suggests adding protein after a rigorous session of long-lasting exercise may reduce the muscle’s muscular damage and muscle soreness created by the exercise session (Saunders, Kane, & Todd, 2004; Saunders, Luden, & Herrick, 2007; Valentine, Saunders, Todd, & Laurent, 2008). It is also important for soccer players to have a strong lower-body muscles to perform at competing levels. Protein supplementation may further increase muscle growth with resistance training exercise. This is of help to soccer players who may see increases in sport performance during a game with protein supplementation. One study showed a significant increase in lower-body strength with a protein supplement taken for 10-weeks (Willoughby, Stout, & Wilborn, 2007). However, less is known about the role of whey protein supplementation on outcomes of interest to team sport athletes. Unlike resistance training or long-distance running, team sports (such as soccer) require a mixture of alternating high- and low-intensity effort. And although findings (Vyazovskiy, 2015) suggest sleep loss can impair muscle recovery, there are no known studies investigating the potential interactions between sleep physiology and nutrition to optimize muscle recovery. Whey protein supplementation is likely important in enhancing performance, recovery, and body composition outcomes in these athletes, but limited trails have been conducted to date, and findings are inconsistent. Furthermore, it is unknown how this sports nutrition strategy would impact teenage athletes.

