**Inclusion Criteria:**

A total of 60 subjects are expected to enroll in this trial with a total of 40 completing the study protocol in its entirety to perform statistical analyses on our primary outcomes. We will recruit soccer players between the ages of 13-18 who are healthy, have no underlying metabolic diseases and have no contraindications to exercise.

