utilizing the track and field team was not a good scientific decision. Thus, we elected to conduct this study on adolescent soccer players.

**Travel to the University of Utah:** Travel via charter buses from Marsh Valley High School in Marsh Valley, ID to the University of Utah, and back to Marsh Valley will be provided free of charge to participants. We will utilize Salt Lake Express bus charter, which is the transportation provider for Marsh Valley High School athletics. The University of Utah's Risk Management Department does not have concerns with this transportation modality (see emails in Other Documents). The charter bus will be paid for utilizing grant funding awarded to the PI ([name]) from the study sponsor (Western Dairy Center).

**Pre-Intervention Procedures:** Before both testing days (pre- and post-intervention) we will ask that all participants record their diet and exercise for 2 days leading up to each of these visits. We will ask that they perform the same diet and activity behaviors that they report before the baseline intervention testing day for the post-intervention testing day. The morning of testing days, before departure from Marsh Valley High School, we will have them consume a study provided granola bar. The granola bar is a Chocolate Chip CLIF BAR® containing 250 calories. Allergens include soy, and may contain peanuts, tree nuts, milk, sesame, and wheat. Student-athletes will report to the Skeletal Muscle Exercise Research Facility in the morning, where they will undergo the following measures:

**Questionnaires:** Athletes will fill out gastrointestinal (GI) and sleep questionnaires. Specifically, the Munich Chronotype Questionnaire (MCTQ) (Shahid, Wilkinson, Marcu, & Shapiro, 2011), Pittsburg Sleep Quality Index (PSQI) (Smyth, 1999), a GI symptom questionnaire (Pereira, Dora IACouto Irving, Susana SLOmer, Miranda CE Powell, Jonathan J. 2014). Participants will fill out a 3-day, 24-hour ASA diet recall at baseline. This data will be uploaded to REDcap.

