## INTERVENTION:

In-season soccer practices and competition will occur 6-days per week across a 10- or 12-week period (pending soccer season length). During the 10- or 12-weeks, participants will consume their assigned supplement or placebo, every day, immediately after practice or competition (or midday on rest days), and immediately before bedtime. Participants will be alerted that it is time to consume their assigned product with a REDCap-delivered text message. Each dose will consist of 20g of whey protein, or 20g of isocaloric control, and will be mixed with 8oz of water in a shaker bottle, which participants will be provided with and will be able to keep at the end of the study. Participants will be provided with a random number of packets of products above the amount they need in order to evaluate compliance. Additionally, they will have a checklist in their bags to mark intake and if they accidentally lost any packets. Study personnel will distribute these bags at the beginning of each month. Participants will store all their empty containers in a separate provided bag, and each bag with

empty containers will be collected to track compliance by study personnel at the end of each month. Time points may vary by  $\pm 1$  week to allow for scheduling flexibility.

Sleep measures: Sleep measures will be evaluated as described above. Sleep measures will be collected at 2-, 4-, 6-, 8-, 10-, and potentially 12-weeks (pending soccer season length) and will be averaged at the end of each of the weeks listed.

Questionnaires: Participants will fill out a 3-day, 24-hour ASA diet recall at 5-, 10- and potentially 12-weeks (pending soccer season length). This data will be put into REDcap. Pittsburgh Sleep Quality Index (PSQI), DOMS questionnaire (Vickers, A. J. (2001)), and the GI symptom questionnaire will be completed at 2-, 4-, 6-, 8-, 10-, and potentially 12-weeks (pending soccer season length). Study personnel will send questionnaires to participants and will use REDCap to complete the questionnaires.

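### Participants' own protein supplements are neither excluded nor limited, and the only record is intermittent diet recall with no stated supplement question and no role in the analysis

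*Combined protocol and SAP*

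**What the plan says.** **Eligibility.** Under Inclusion Criteria, players must be "healthy, have no underlying metabolic diseases and have no contraindications to exercise", aged 13 to 18, and from one high school's soccer teams. The Exclusion Criteria name "non-adolescents; untreated or underlying metabolic or cardiovascular diseases; allergies to dairy", followed by a list of allergens in the study-provided food. Neither list mentions protein or other supplements.

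**Contrast.** The Intervention section states "Each dose will consist of 20g of whey protein, or 20g of isocaloric control", taken at two times each day for 10 or 12 weeks. It says nothing about protein products from outside the study.

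**Diet recording.** Under Procedures, "Participants will fill out a 3-day, 24-hour ASA diet recall at baseline". In the Intervention section, "Participants will fill out a 3-day, 24-hour ASA diet recall at 5-, 10- and potentially 12-weeks". Before the two testing visits, "we will ask that all participants record their diet and exercise for 2 days leading up to each of these visits", and players are asked to repeat the baseline pattern before post-testing.

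**Adherence.** Packet counts and a checklist follow the study product. The urine samples at weeks 4 and 8 are a sham and are discarded unmeasured.

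**Analysis.** The statistical section specifies a group-by-time repeated measures ANOVA with follow-up t-tests. Diet data do not appear there in any role.

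**The concern.** The tested exposure is a product that athletes can obtain for themselves. The Background says "Protein supplementation and whey protein in particular, is a common sports nutrition strategy", so own use is foreseeable. As written, a player who already takes whey is eligible, and nothing in the protocol asks that player to stop or declare it.

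A control player who takes whey receives some of the experimental exposure. Randomisation balances prior users between arms on average. It does not restore the contrast if extra protein does less for someone who already takes it. The bias is then toward no effect. The statistical section also says this sample will feed sample-size calculations for a later trial, so a diluted estimate would be carried forward.

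**Working it through.** **1. Coverage of the diet records.** Over 10 weeks there are 10 × 7 = 70 intervention days. Recalls at weeks 5 and 10 sample 2 × 3 = 6 of them. The 2-day record before post-testing adds at most 2, giving 8/70 = 11%. Over 12 weeks, with a third recall, the figure is (9 + 2)/84 = 13%. Own use could be seen on those days if players report it. On the other days no planned measure would show it.

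**2. The plan's own power figure.** The statistical section claims more than 90% power with 20 per group, but states no planning effect or SD, so the figure cannot be reproduced. With a two-sided alpha of 0.05 (sidedness is not stated) and a two-sample t-test on post-test values, 20 per group gives:

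| Standardised effect | Power |
|---|---|
| 0.20 | 10% |
| 0.50 | 34% |
| 0.80 | 69% |
| 1.05 | 90% |

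The first three effects are the plan's generic small, medium and large labels. None is a planning value.

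**3. Dilution.** Let c be the share of controls using their own product and f the fraction of the study-product effect that it gives them. Assume that users in the whey arm gain nothing extra. Then:

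effective difference = 0.80 × (1 − f × c)

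The documents give no value for c or f, so both are varied.

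| c | Difference, f = 1 | Power | Difference, f = 0.5 | Power |
|---|---|---|---|---|
| 0% | 0.80 | 69% | 0.80 | 69% |
| 10% | 0.72 | 60% | 0.76 | 65% |
| 20% | 0.64 | 51% | 0.72 | 60% |
| 30% | 0.56 | 41% | 0.68 | 55% |

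For f = 1, the sample needed to offset the dilution grows by 1/(1 − c)²: 1.23, 1.56 and 2.04 times at 10%, 20% and 30%.

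**4. Sensitivity to the starting point.** Both checks keep f = 1.

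- *Change scores.* Assume a pre-post correlation of 0.7. The SD of change is √(2 × (1 − 0.7)) = 0.775 SD, so 0.80 becomes 0.80/0.775 = 1.03 on that scale. Power starts at 89% and falls to 82%, 72% and 61%.
- *The effect that gives exactly 90%.* Starting at 1.05 SD, power falls to 83%, 74% and 62%.

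The starting power depends heavily on the assumptions. The loss at c = 10% is 7 to 9 points in all three versions.

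**The case against.** **Intake is recorded.** A reader might infer that own protein use goes wholly unrecorded, or that a null result could never be told apart from contamination. The documents do not support either reading. A shake is dietary intake, and recalls in both arms at baseline and weeks 5 and 10, plus the 2-day records, allow a partial comparison of protein intake by arm. What stands is that the sampling is sparse, no supplement question is stated, and no analysis is named.

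**Use by these players is not shown.** The Background sentence goes on to refer to resistance training and describes sports nutrition in general. Nothing gives a rate for adolescents at this school, so own use is foreseeable but not demonstrated. Consent and assent forms go home with families and are not in the text reviewed. They may say something about supplements.

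**The illustration is at the upper end.** It takes 0.80 SD from a label, gives own use the full effect of a twice-daily product, lets whey-arm users gain nothing extra, and ignores the planned pre-post analysis. If use is balanced and effects simply add, the contrast is not diluted at all. All of this stands, and the percentages should not be read as a forecast.

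**Usual intake is a legitimate background.** Whey added to whatever players normally eat is a fair question, and a strict exclusion would shrink a single-school pool that must supply 60 players. This stands against a mandatory exclusion. It does not weaken the case for asking about use and reporting it.

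**Conclusion.** The point holds as a cheap improvement that the sponsor should make. The protocol has no eligibility rule and no intervention-period limit on own protein products. Its only record is intermittent recall, covering roughly 11% to 13% of intervention days, with no stated supplement question and no analytic use. Any dilution would run toward no effect.

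Its size is unknown. Under the post-only 0.80 SD illustration, 10% to 30% use in controls costs about 9 to 28 percentage points of power if own use has the full effect, and about 4 to 14 points if it has half. The loss is zero if use is balanced and effects add. The gap in the text is certain. The amount of contamination is not.

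**What to change.** 1. **Exclusion Criteria and Intervention.** Ask participants to agree to go without non-study protein or amino-acid supplements from baseline to post-test. Make unwilling users ineligible only if the single-school pool allows it.
2. **Baseline questionnaires.** Ask about current use of such products.
3. **Two-weekly REDCap questionnaires.** Add one yes/no item on non-study protein products.
4. **Statistical section.** Report that use, and total protein intake from the recalls, by arm. Prespecify a sensitivity analysis that takes non-study use into account. Keep the as-randomised comparison primary, because use after randomisation may itself be affected by assignment.

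**Cost.** A baseline question, one item on forms that are already sent, and a few sentences of text. Some players may be asked to pause their own product, or may be ineligible if the optional exclusion is adopted. If recruitment is tight, steps 2 to 4 alone would make contamination visible.

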**Design**

---

Blinded Trial (Single or Double Blinded)  
Placebo Controlled Trial  
Randomized Trial

**Study Procedures**

---

**Recruitment/Participant Identification Process:**

In the Spring and Summer of 2022, student-athletes on a high school soccer team, and their parents will be informed of the trial by members of the study team at in in-person informational meeting. Study personnel will go over study information and protocol in detail at this time, and no coaches will be involved with this meeting. We will provide a copy of the consent and assent documents for parents and athletes to take home. If parents and athletes want to be part of this study, we will consent individually over Zoom.

**Informed Consent:****Description of location(s) where consent will be obtained:**

Parental informed consent and permission, and participant assent (for participants under the age of 18) and informed consent (for participants 18 years of age) will be obtained over Zoom.

**Description of the consent process(es), including the timing of consent:**

Parental informed consent and permission and participant assent or participant informed consent will be completed over Zoom, with a member of the study team and the potential participant, and their parent, if applicable. This will follow the in-person information session where the study is explained to participants and parents and copies of the consent and assent forms are provided for them to take home and review prior to scheduling an informed consent visit. During the explanation of the details of the Informed Consent, Parent Permission and Assent documents, athletes and their parents will be given the opportunity to voice their questions and concerns. Also, potential participants will be briefed on confidentiality and will be asked to not talk with their teammates or peers that they are involved in this study. Each participant will be asked to not repeat any identifying or personal information about other

teammates that may be with them on their study day. Additionally, a make-up day for baseline and post-intervention testing will be in place on the UofU campus so coaches and other athletes will not be made aware of who is and is not participating, because not everyone who participates will be going on the same study day. Coaches will not be involved in the consent process and will not be told who is and is not participating in the research study. Coaches will be instructed not to ask their athletes about the research study or if they are participating. Because baseline testing and post-season testing are not during the soccer season, coaches will not know who is going to be participating. On days when study personnel pick up and distribute supplement packets, participants will be instructed to report to the gymnasium of their High School, away from their coaches and other peers. Potential participants, and parents, will be told that they are free to take more time to decide if they wish to participate/allow their child to participate; and informed that they can withdraw consent and assent at any time after enrolling in the trial.

### **Procedures:**

**Informed Consent, Parental Permission and Assent:** These will be obtained over Zoom, prior to participation in any study procedures.

**Randomization:** Randomization will occur following pre-intervention testing. Participants will be randomized via random number generator stratified by sex, and blinded into either whey protein supplement group or placebo (isocaloric) control group.

**Pre- and Post-Intervention Testing Background:** Pre- and post-intervention testing will occur over a single day for each participant at the University of Utah campus. There will be three (3) separate days of pre-intervention and post-intervention testing. One day will be for members of the “Girls’ Soccer Team”. One day for members of the “Boys Soccer Team”. The final day will be a make-up day for participants who were unable to attend with their team, but wish to participate. According to the coaches, no student-athletes openly identify as non-binary nor transgender. However, in March of 2020 Idaho’s “Fairness in Women’s Sports Act” was signed in to law. While it has yet to go in to effect, if taken up, it will prohibit transgender women and girls from competing on teams that align with their gender identity in Idaho. Thus, it is possible that individuals may not be open about this. To address concerns re: outing anyone, participants will complete the testing day on their team’s assigned day, as mentioned above, or on the make-up day if they are not available on the main testing day. Furthermore, our strategy of having make-up testing options for both pre- and post-intervention means that not all members of each team will be tested on the same day. Thus, this mitigates potential risk of coercion as teammates will not know for sure who elected to participate or not in the trial.

**Selection of School:** Marsh Valley High School in Marsh Valley, ID was selected as the test site for this study due to the following connection:

The Track and Field coach at this school comes from a family of Dairy farmers and is also a Paralympic athlete who has had a relationship with the Western Dairy Center (study sponsor) for a number of years. He inquired with WDC about doing a trial on his student-athletes, so the WDC connected the PI ([name]) with this school for the trial. Due to large differences in athlete type and training load in track and field (sprinters, distance, jumpers, throwers),

utilizing the track and field team was not a good scientific decision. Thus, we elected to conduct this study on adolescent soccer players.

**Travel to the University of Utah:** Travel via charter buses from Marsh Valley High School in Marsh Valley, ID to the University of Utah, and back to Marsh Valley will be provided free of charge to participants. We will utilize Salt Lake Express bus charter, which is the transportation provider for Marsh Valley High School athletics. The University of Utah's Risk Management Department does not have concerns with this transportation modality (see emails in Other Documents). The charter bus will be paid for utilizing grant funding awarded to the PI ([name]) from the study sponsor (Western Dairy Center).

**Pre-Intervention Procedures:** Before both testing days (pre- and post-intervention) we will ask that all participants record their diet and exercise for 2 days leading up to each of these visits. We will ask that they perform the same diet and activity behaviors that they report before the baseline intervention testing day for the post-intervention testing day. The morning of testing days, before departure from Marsh Valley High School, we will have them consume a study provided granola bar. The granola bar is a Chocolate Chip CLIF BAR® containing 250 calories. Allergens include soy, and may contain peanuts, tree nuts, milk, sesame, and wheat. Student-athletes will report to the Skeletal Muscle Exercise Research Facility in the morning, where they will undergo the following measures:

**Questionnaires:** Athletes will fill out gastrointestinal (GI) and sleep questionnaires. Specifically, the Munich Chronotype Questionnaire (MCTQ) (Shahid, Wilkinson, Marcu, & Shapiro, 2011), Pittsburg Sleep Quality Index (PSQI) (Smyth, 1999), a GI symptom questionnaire (Pereira, Dora IACouto Irving, Susana SLOmer, Miranda CE Powell, Jonathan J. 2014). Participants will fill out a 3-day, 24-hour ASA diet recall at baseline. This data will be uploaded to REDcap.

**Anthropometrics and Body Composition Assessment:** In a private room, all athletes will undergo non-invasive measurements of height and weight (which will be used to calculate BMI-percentile) (Kuczmarski, 2002). Each athlete will next be measured for body composition via the BodPod. The BodPod requires participants to wear spandex-like material or a sport-style bathing suit for the body composition assessment. Participants will be required to change into these clothing materials as well as wear a swim cap to cover the hair (as is required for this equipment). They will change in a private bathroom that is located in the same private room where the BodPod is located. Importantly, the scale in which participants will have their weight measured on does not have a display. The weight is displayed only on the computer, which participants will not see. Participants will not be provided with their BodPod results, and will not be aware of their weight, BMI percentile, nor body composition. As it is done in private, no other participants will see other's weight or body composition either. Participant body composition and anthropometric forms will be printed at a later time by study staff and added to participant folders and our REDcap Data Set when participants have left.

**Blood Sample:** A blood sample will be obtained via the antecubital vein, by a trained member of the CTSI Clinical Services Core (CSC). The sample will consist of about a tablespoon of blood. We will use blood samples to measure the following biomarkers: IL-6, follistatin,

adiponectin, FGF21, decorin, and cathepsin B (CTSB)(Chow et al., 2022). IL-6 will be measured to assess systemic inflammation. Follistatin is measured to assess long-term muscle growth. Adiponectin is measured to assess inflammation. FGF21 is measured to assess the function of various metabolic pathways. Decorin is measured to assess inflammation. CTSB is measured to assess correlating protein levels in the blood. Blood samples will be centrifuged, and plasma samples will be stored in a -80-degree freezer for batch analysis at the end of the study. Study provided bagels will be distributed after the blood draw.

**Cardiorespiratory Fitness Testing:** Athletes will then be escorted by study personnel to the university track and field to begin field testing. Athletes will perform a *1.5-mile test*, and a *30-yard sprint* test to measure fitness. The purpose of the 1.5-mile test is to evaluate how fast athletes can run, covering an allotted distance. This test will measure how much oxygen is being used by the muscle in a field test. The purpose of the sprint test is to assess athletes rapidly accelerating from a standing position and to measure their maximal speed over a short distance.

**Muscular Fitness Testing:** Finally, athletes will perform muscle strength and endurance tests. Muscle endurance will be measured by having our participants contract their leg muscles against a specific force at a particular speed for a certain number of repetitions. Muscle strength will be assessed by having the participants contract their leg muscles with as much force as possible against a non-movable bar.

**Sleep measures:** After baseline testing ends, and before participants leave, each participant will be provided with a Fitbit® watch (Inspire 2). Fitbit's will be used measure sleep efficiency, duration, regularity, timing, and staging, similar to prior studies. We will use a program called Fitabase to collect the data from each Fitbit®. Participants will be instructed to wear their Fitbit® for 1-week straight (except during training times and when they are showering/getting wet) so that baseline sleep habits can be evaluated. Participants will be able to keep their Fitbit® after the study ends.

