
## Purpose and Objectives

---

The overall aim of the proposed project is to compare protein supplementation on performance, recovery, and body composition changes in adolescent soccer players between the whey protein and the control group in response to the 10-week intervention. Hypothesis: We hypothesize that the whey protein group will demonstrate more favorable changes in

performance, recovery, and body composition outcomes than the control group following the 10-week supplementation period.

Secondary outcomes will include investigating interactions between sleep physiology and dietary protein on muscle recovery and performance following the 10-week intervention.

*Hypothesis:* Sleep efficiency will be higher in the whey protein supplementation group versus the placebo control. *Exploratory* analyses will examine the impact of whey protein supplementation on dimensions of sleep including duration, regularity, satisfaction, alertness, timing, and sleep staging (e.g., stage N1, N2, SWS, rapid eye movement (REM))

The **expected outcomes** will provide support for whey protein supplementation to enhance exercise performance, recovery, and body composition in adolescent, team-sport athletes. Completion of the proposed objectives (see below) will add to the sparse evidence base on protein supplementation in this unique, athletic population, and provide preliminary data for future investigations in this area. Specifically, future work could address both mechanistic questions as well as evaluation of other protein options, such as milk consumption, which could be a more cost-effective and acceptable option for youth athletes.

Objective 1: Compare the impact of 10-weeks of whey protein vs. isocaloric control on performance in high school soccer players.

Objective 2: Compare the impact of 10-weeks of whey protein vs. isocaloric control on body composition in high school soccer players.

Objective 3: Compare the impact of 10-weeks of whey protein vs isocaloric control on hunger and satiety in high school soccer players

Objective 4: Compare the impact of 10-weeks of whey protein vs. isocaloric control on sleep duration and quality in high school soccer players.

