Urine Samples: We will randomly assign participants to provide urine samples at weeks 4 and 8 as a sham adherence measure. These samples will be discretely disposed of following collection and will not be saved nor stored. We are using this method as a sham adherence measure so that participants will think that we can know if they are consuming their allotted supplement, which may help with their compliance. We will tell participants at the end of the study we did not take any measurements from their urine samples.

Post-testing will be the same as pre-testing and will commence after the 10- or 12-weeks (pending soccer season length). All measures described above in Pre-Intervention testing will take place again, with the exception of a week of Fitbit® monitoring following completion of the 10- or 12-week (pending soccer season length) intervention.

Debrief: Following completion of post-intervention testing, participants will be debriefed (see Debrief Document in Other Documents) regarding the sham urine collections which were used to increase adherence.

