### **Procedures performed for research purposes only:**

## **Statistical Methods, Data Analysis and Interpretation**

---

A two-way (group x time) repeated measures analysis of variance (ANOVA) will be used to compare change between groups in body composition, performance, and recovery. If a significance in group x time interactions occur, an independent t-test will be performed for each dependent variable between groups. An alpha level will be set at  $p < 0.05$ .

Sample size and power analysis: For a total of 60 participants, we anticipate a 30% attrition, leaving us with  $n=40$  ( $n=20$  per group). This provides  $>90\%$  power for detecting differences in our main outcome variables. Based on preliminary data, a similar study used  $n=18$  for their sample sizes. This sample size will be used for sample size calculations for a future well-

powered trial. Estimates for effect sizes will be implemented due to the limited sample size. Effect sizes ( $n^2$ ) will be defined as small (0.20), medium (0.50), and large (0.80).

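### Six blood markers are measured before and after the intervention but assigned to no numbered objective, and the only stated analysis, an ANOVA with no stated scale, is less efficient than a baseline-adjusted log-scale analysis if the markers are right-skewed

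*Combined protocol and SAP*

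**What the plan says.** The Blood Sample paragraph under Procedures says "We will use blood samples to measure the following biomarkers: IL-6, follistatin", and goes on to adiponectin, FGF21, decorin and cathepsin B, with a one-line purpose for each. The INTERVENTION section says "Post-testing will be the same as pre-testing and will commence after the 10- or 12-weeks", so each marker has a baseline and a follow-up value.

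In Purpose and Objectives the overall aim is to "compare protein supplementation on performance, recovery, and body composition changes in adolescent soccer players". Objectives 1 to 4 cover performance, body composition, hunger and satiety, and sleep. None names a blood marker, inflammation or recovery. Background and Introduction does supply a link: "Muscle recovery is regulated, in part, by nutrient availability, hormones, and inflammation".

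Statistical Methods, Data Analysis and Interpretation gives one method. A two-way repeated measures ANOVA "will be used to compare change between groups in body composition, performance, and recovery". If the interaction is significant, "an independent t-test will be performed for each dependent variable between groups". The significance level is 0.05. The section mentions no marker, transformation, distribution check or baseline adjustment.

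**The concern.** Two gaps combine. First, the markers have no declared role. If they count as recovery outcomes, the ANOVA applies to them; if they do not, they have no analysis at all.

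Second, no scale is stated. A plasma concentration cannot be negative and is often right-skewed. That is general knowledge; the documents do not show it for these six. On the raw scale a few high values dominate the variance of the change, and the effect is expressed as a difference where a percentage change may be the more natural summary. With about 20 athletes per group, one or two of them could drive the result.

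At stake is how much is learned from two venous samples per participant, aged 13 to 18. With role and scale open, the choice between raw and log could also be made after the data are seen, six times over.

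**Working it through.** **The plan's own power figure.** The plan claims more than 90% power for its main outcomes with 20 per group. It gives no effect size, SD or correlation, so the figure can be neither reproduced nor refuted, and it is not stated for the markers. For orientation, a two-sided two-sample t-test at 0.05 with 20 per group has 69% power at a standardised effect of 0.8 and needs 1.05 for 90%.

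**Inputs from the documents.** Six markers, two occasions, 20 completers per group, alpha 0.05 (taken as two-sided). The value 0.8 appears only as the plan's label for a large effect; it is borrowed here as an illustration.

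**Inputs assumed.** Lognormal marker; pre-post correlation r of 0.5 to 0.7 on the log scale; coefficient of variation (CV) of 31%, 50% or 100%; effect of 0.8 SD of log change, down or up.

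**Step 1: the planned test.** With two occasions, the group-by-time interaction is the same test as a t-test on change scores.

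**Step 2: scale.** Log SD is s = √ln(1 + CV²), giving 0.30, 0.47 and 0.83. The SD of log change is s√(2(1 − r)). The effect as a ratio against control is exp(±0.8 × s√(2(1 − r))). For a fall at CV 100% this is exp(−0.8 × 0.83) = 0.51 at r = 0.5, and exp(−0.8 × 0.83 × 0.775) = 0.60 at r = 0.7.

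**Step 3: what baseline adjustment adds.** The ANCOVA residual SD on the log scale is s√(1 − r²). The standardised effect therefore grows by √(2(1 − r)/(1 − r²)) = √(2/(1 + r)):
- r = 0.5: 0.8 × 1.155 = 0.92
- r = 0.7: 0.8 × 1.085 = 0.87

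**Step 4: simulated power** (20,000 trials per setting; ANCOVA with baseline only, sex omitted; ranges span r = 0.5 and 0.7):

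| CV | Raw change, marker falls | Raw change, marker rises | Log change | Log ANCOVA |
|---|---|---|---|---|
| 31% | 61-62% | 70-72% | 69-70% | 74-81% |
| 50% | 53-55% | 66-70% | 69-70% | 74-81% |
| 100% | 38-39% | 54-60% | 69-70% | 74-81% |

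With no true effect, rejection is about 4-5% for every method.

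**Reading the table.** Log ANCOVA beats the raw change test in every setting. For a rising marker with CV up to 50%, the log scale alone gains little or nothing, and the gain comes from baseline adjustment. For a falling marker, or at high CV, both contribute.

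**The case against.** Several counter-arguments have force.

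- **Recovery may cover the markers.** The overall aim and the ANOVA sentence both name recovery, and the background ties recovery partly to inflammation. A reader might infer that the markers serve no aim at all; the text does not support that. What stands is that they are never assigned, and the purposes given for FGF21 (metabolic pathways) and cathepsin B (protein levels in blood) are hard to read as recovery.
- **The loss depends on direction.** It would be tempting to quote the falling-marker losses at CV 50-100% as the general cost. The plan states no expected direction for any marker. A fall may be the favourable change for IL-6, described as a measure of systemic inflammation; follistatin is there for muscle growth, where a rise may be.
- **The assumed effect is large.** At CV 100% it means a 40-49% fall against control. No passage supports an effect of that size.
- **The follow-up t-test.** One might infer that requiring it as well lowers power further. That holds only if it is run on post-test values. Run on change, it repeats the interaction test, and the plan does not say which.
- **Silence is not prohibition.** Nothing in the plan forbids a log transformation, type I error is not inflated, and the plan presents the sample as input to a later, well-powered trial.

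These points limit the size and urgency of the concern. They do not remove it: an unassigned, unscaled analysis of six markers remains, and the better method uses only data already collected.

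**Conclusion.** The point holds as one of efficiency and prespecification. Six markers are measured twice, no numbered objective names them, and the single stated method has no scale and no baseline adjustment.

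Under the assumptions listed, raw change power is about 38-62% for a falling marker and 54-72% for a rising one, against 74-81% for log-scale ANCOVA in both directions. These figures illustrate a range. They rest on lognormality, the CVs, the correlations and the 0.8 effect, none of which the documents give as design values for the markers. A reader should not conclude that the planned test is invalid, or that every marker would lose power by moving from raw change to log change alone.

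The change should be made, but it does not touch the performance or body composition outcomes.

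**What to change.** Add to Statistical Methods, Data Analysis and Interpretation:

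> The six blood markers are exploratory. Each will be log-transformed and compared between arms by ANCOVA on log post-test value with log baseline and sex, reported as a ratio of geometric means with 95% CI.

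Sex belongs in the model because randomization is stratified by it. If some markers are instead meant as recovery outcomes, Purpose and Objectives should say which.

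The cost is a few sentences, with no extra samples or visits. The small downside is that results are read as ratios.

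Two optional additions: a rule for values below the assay limit, since a log needs a positive value; and running each athlete's two samples on the same plate, with both arms on every plate, within the batch analysis already planned for the end of the study. No harm from plate allocation has been shown, so the plate map is only a suggestion.
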